6.4.2 Analysis of Secondary Efficacy Endpoints

Descriptive statistics (n, mean, SD, minimum, median, maximum) and the same primary efficacy analysis (ANCOVA) as for the primary endpoint will be applied to change from baseline at the end of the 12-week treatment period in children (5 to <12 years of age) for:

- Mean volume voided per 24 hours
- Maximum volume voided
- Mean number of daytime incontinence episodes per 24 hours
- Mean number of daytime micturitions per 24 hours

Change from baseline in the number of dry (incontinence free) days per 7 days at the end of the 12-week treatment period will be analyzed with a negative binomial regression model including treatment group, sex, geographical region as factors and the log baseline rate of number of dry days (e.g., the log of the ratio of dry days and number of diary days at baseline) as covariate.

Data of these secondary efficacy endpoints will be analyzed both without imputation and with imputation using the LOCF method, for the FAS.

The same analysis detailed in Section 6.4.1.3 will be performed for all the secondary efficacy endpoints on the FAS as sensitivity analysis.

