9.4.2 Analysis of Secondary Endpoints

The same analysis (ANCOVA) as for the primary endpoint will be applied to change from baseline at the end of the 12-week treatment period in children (5 to \leq 12 years of age) for:

- Mean volume voided per 24 hours
- Maximum volume voided
- Mean number of daytime incontinence episodes per 24 hours
- Mean number of nighttime incontinence episodes per 24 hours
- Mean number of daytime micturitions per 24 hours

Change from baseline in the number of dry (incontinence free) days per 7 days at the end of the 12-week treatment period will be analyzed with a negative binomial regression model including treatment group, sex, geographical region as factors and the log baseline rate of number of dry days (e.g., the log of the number of dry days divided by number of diary days at baseline) as covariate.

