2.3 Randomization

Subjects will be entered into the interactive response technology (IRT) system at screening and assigned a subject number. At Visit 3 (baseline) randomization will be performed via the IRT system and treatment assigned in a 1:1 ratio to mirabegron or placebo. Prior to the initiation of the study treatment, on day 1, the site staff will contact the IRT system in order to determine the randomly assigned treatment. Subjects will be stratified by age category: 5 - <12 years and 12 - <18 years of age.

Subjects will be assigned a subject number at study entry (i.e., signing the ICF/assent). The subject numbers will be sequential and rising. The subject number will comprise of 10 digits; 5 digits for the site number (provided by the sponsor) and 5 digits for the consecutive subject number.

Subjects will be randomized to receive IP according to the randomization schedule obtained via the IRT system. The study site personnel will dispense the treatment according to the IRT system's assignment. Specific procedures for randomization through the IRT system are contained in the study procedures manual.

An enrolled subject who withdraws or discontinues before dosing or before randomization will be considered a screen failure. Randomized subjects who withdraw or discontinue will not be replaced.

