3 SAMPLE SIZE

Efficacy of mirabegron in children will be based on both primary and secondary endpoints. Given the clinical hurdle to demonstrate efficacy in a population challenging to recruit, an alpha-level of 10% would appear reasonable and justified. In a study with propiverine in children, Marschall-Kehrel (2009) showed a difference in mean number of micturition episodes/24 hours of 0.8 between propiverine and placebo, with a standard deviation (SD) between 2.2 and 2.3. Assuming at least similar efficacy of mirabegron, with a treatment effect of 0.9 micturitions per day between mirabegron and placebo and a common SD of 2.3, a sample size of 82 evaluable subjects (children) per treatment group would provide a power of 80%.

These assumptions, together with levels for Type-1 error and power were agreed upon with Pediatric Committee in the current Pediatric Investigation Plan.

Under the assumption that after randomization about 10% of the subjects will not be evaluable for the analysis of the primary endpoint (i.e., not fulfilling the criteria for inclusion in FAS), at least 184 children (5 to < 12 years of age) must be randomized in order to have at least 164 evaluable children for the analysis of the primary efficacy endpoint. For adolescents, no formal sample size will be calculated, at least 32 adolescents (12 to <18 years of age) must be randomized, yielding at least 16 adolescents on mirabegron.

Further assuming a 50% screen failure rate, approximately 368 children have to be enrolled to achieve 184 children (5 to <12 years of age) randomized and approximately 64 adolescents will be enrolled to achieve at least 32 adolescents (12 to <18 years of age) randomized (at least 92 children and 16 adolescents must be randomized to mirabegron).

Recruitment will continue until the minimum number in both children and adolescents has been achieved.

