5.2.4 Mean Number of Daytime Micturitions per 24 hours

For a week day the daytime micturitions will be derived from "Number of Times using the Toilet During the Day" was entered into the 5-day Week Diary.

For a weekend day the daytime micturitions will be derived from the number of times a "Pee in Toilet" or a "Pee in Toilet and Leakage" was entered into the 2-day Weekend Episodic Diary between the time the subject woke-up (exclusive) and went to sleep (inclusive). However, the first micturition occurring at or after the time of wake-up it is considered a nighttime micturition, see Section 5.1.

The total number of micturitions per weekend day is equal to the total number of times, in the diary, an amount of pee was recorded during daytime for that day.

For each subject, the mean number of daytime micturitions at Visit x (x=4, 5, 6, and 7) in the week before the visit will be calculated as:

Sum of the Number of Daytime Micturitions (per day) over the Valid Diary Days prior to Visit x Number of Valid Diary Days

5.2.5 Number of Dry (incontinence free) Days per 7 Days at the End of the 12-weeks Treatment Period

For a week day a "Dry (incontinence free) Day" is defined as a day where the response is "Dry" to the question "How was your Day" and to "How was your Night".

Let D_{dry} be the number of valid diary days where the response to both questions was "Dry". Let D_{wet} be the number of valid diary days where the response to one of the two questions or to both questions was "Wet".

For a weekend day a "Dry (incontinence free) Day" is defined as a day where no "Leakage" and no "Pee in toilet and leakage" are reported. A "Wet (incontinence) Day" is defined as a day where a "Leakage" or a "Pee in toilet and leakage" is reported.

If $(D_{dry} + D_{wet}) > 3$, then the number of dry days per 7 days at Visit 7 will be calculated for a subject as:

 $\frac{D_{dry}}{(D_{dry}+D_{wet})} \times 7$, otherwise its value is missing.

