6 STATISTICAL METHODOLOGY

6.1 General Considerations

Efficacy data will be summarized for each age group (children [5 to <12 years of age] and adolescents [12 to <18 years of age]) by treatment group and visit, and safety data will be summarized for each age group and overall, by treatment group and visit, unless otherwise specified.

In general, continuous data will be summarized descriptively including the number of subjects (n), mean, standard deviation (SD), median, minimum and maximum. Categorical data will be summarized by frequencies and percentages. Percentages by categories will be based on the number of subjects with no missing data, i.e. the percentages for the non-missing categories will add up to 100%.

All statistical comparisons will be conducted using 2-sided tests at the 10% significance level unless stated otherwise. All null hypotheses will be of no treatment difference, all alternative hypotheses will be two-sided, unless specifically stated otherwise.

All data summarization and analyses will be performed using SAS® Version 9.4 or higher on Red Hat Enterprise Linux. Specifications for table, figure, and data listing formats can be found in the TLF specifications.

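### Dry days per week cannot exceed 7 but is analysed with a negative binomial model, so its nominal 10% test may run anywhere from about 4% to about 12%, depending on a distribution the plan does not give

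*SAP*

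**What the plan says.** SAP 5.2.5 counts dry and wet days in the diary week. If more than three days are classified, "then the number of dry days per 7 days at Visit 7 will be calculated for a subject as" dry/(dry + wet) × 7; otherwise the value is missing. The result is a rescaled proportion, for example 3 dry days of 5 gives 4.2, with a floor of 0 and a ceiling of 7.

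For the test, SAP 6.4.2 states that the endpoint "will be analyzed with a negative binomial regression model including treatment group, sex, geographical region as factors", with the log of the baseline dry-day rate as covariate. Protocol 9.4.2 agrees: it "will be analyzed with a negative binomial regression model" with the same terms. Neither specifies a scale parameter, a robust standard error or another protection against a wrong variance function.

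The significance level comes from SAP 6.1: "All statistical comparisons will be conducted using 2-sided tests at the 10% significance level unless stated otherwise". SAP 6.4 makes no multiplicity adjustment. SAP 6.4.2 also applies the sensitivity analyses of 6.4.1.3 to every secondary endpoint. Neither document gives an expected mean, variance or distribution for dry days.

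**The concern.** A negative binomial describes an unbounded count with variance μ + αμ², α ≥ 0. The variance therefore grows steadily with the mean and cannot fall below it. For a share of a week the variance shrinks again as the mean nears 7. If the fitted variance exceeds the true one, the model-based standard error is too large, the 90% interval too wide and the p-value too high. Both documents say that efficacy in children rests on the primary and the secondary endpoints together, so a real gain in dry days could be understated in the analysis planned to show it.

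**Working it through.** **Inputs from the documents.** Two-sided 10% (SAP 6.1), 1:1 allocation (SAP 2.3), 82 evaluable children per arm (SAP 3), 4 to 7 classified days (SAP 5.2.5). The sample size is set on the primary endpoint, "with a treatment effect of 0.9 micturitions per day between mirabegron and placebo and a common SD of 2.3". It reproduces:

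- n per arm = 2(1.645 + 0.842)² × 2.3²/0.9² = 80.8, so 81
- power at 82 = Φ(0.9/(2.3√(2/82)) − 1.645) = Φ(0.861) = 80.5%
- 82/0.90 = 91.1, so 92 per arm and 184 randomized

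No stated figure exists for the dry-day test, so everything below rests on assumptions.

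**Why the variance can be wrong.** Let p be the dry share at week 12 and ρ the correlation between days within a child. With 7 days, μ = 7p and the true variance/mean is (1 − p)(1 + 6ρ). The negative binomial fits 1 + αμ.

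- *High share, weak clustering* (p = 0.60, ρ = 0.1): true ratio 0.4 × 1.6 = 0.64. The model cannot go below 1, so the standard error is inflated by √(1/0.64) = 1.25. Simulation gave 1.253. The implied size is 2[1 − Φ(1.645 × 1.253)] = 3.9%; simulated 4.1%.
- *Strong clustering* (p = 0.45, ρ = 0.5, μ = 3.15): the many all-wet weeks push the fitted dispersion to about 0.545, so the model implies 1 + 0.545 × 3.15 = 2.72 against a true ratio of 0.55 × 4 = 2.20. Inflation is √(2.72/2.20) = 1.11; simulated 1.10, with size 7.3%.
- *Low share, moderate clustering* (p = 0.15, ρ = 0.35): simulated SE ratio 0.997, size 10.3%.

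**Size of the nominal 10% test.** Assumptions: beta-binomial dry days, 80% of diaries with 7 valid days, baseline dry share 0.10-0.15, latent baseline/week-12 correlation 0.3-0.7. Model: maximum-likelihood negative binomial with treatment, sex, region and log baseline rate, Wald test. The week-12 value was the response and 0.5 was added to the baseline rate's numerator and denominator, because a negative change and log 0 cannot be fitted. There were 2,000 to 6,000 runs per cell (Monte Carlo error 0.4-0.7 points).

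| Week-12 dry share | ρ 0.1 | ρ 0.2 | ρ 0.35 | ρ 0.5 | ρ 0.7 |
|---|---|---|---|---|---|
| 0.15 | 10.3-11.6% at every ρ | | | | |
| 0.30 | 10.0% | 9.6% | 9.2% | 7.7% | 6.2% |
| 0.45 | 7.9% | 10.6% | 8.9% | 7.3% | 5.2% |
| 0.60 | 4.1% | 8.2% | 10.0% | 8.9% | 6.0% |

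ANCOVA on the same data gave 9.4-11.1% at shares of 0.30 or more, and 10.4-12.0% at 0.15.

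**Power, negative binomial against ANCOVA** (2,500 runs; assumed gains of 0.10 to 0.15 in dry share, that is 0.7 to 1.05 days):

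| Share, ρ | Negative binomial | ANCOVA |
|---|---|---|
| 0.15, 0.35 | 79% | 80% |
| 0.30, 0.2 | 78% | 78% |
| 0.45, 0.35 | 75% | 77% |
| 0.30, 0.5 | 71% | 77% |
| 0.45, 0.5 | 68% | 75% |
| 0.60, 0.7 | 72% | 80% |
| 0.45, 0.7 | 62% | 75% |

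**Check of the proposed model.** A further 28 scenarios with the planned covariates (1,200 null and 500 power runs each) gave size 4.0-10.0% for the negative binomial and 7.8-11.7% for a quasi-binomial. For a gain of 0.84 day, negative binomial power ranged from 1 point above to 16 points below (share 0.45, ρ 0.7: 45% against 61%).

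**Rescaling.** At share 0.45 and ρ 0.35, size was 9.0% with all 7 days valid and 8.9% with rescaled shorter diaries. The ceiling drives the effect.

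**The case against.** The strongest case against is that no particular error rate can be read from the plan. That stands. A reader might infer that the standard errors are always too large and that the test really runs at 5-9%. The documents do not support this: they give no dry-day distribution, and with few dry days at week 12 the test is nominal or slightly liberal. Simulations that omit the planned covariates also exaggerate the conservatism (at share 0.30 and ρ 0.5, 4.7% without them and 7.7% with them).

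A reader might also infer that non-integer values, or giving a 4-day diary the weight of a 7-day diary, cause the problem. Rescaling hardly changes size. With clustered days, equal weighting is nearly efficient: at ρ = 0.5 the variance of a child's proportion is proportional to 2.5/4 = 0.625 for 4 days and 4/7 = 0.571 for 7 days, a ratio of only 1.09.

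The SAP 6.4.1.3 analyses, which SAP 6.4.2 extends to this endpoint, include ANCOVA without imputation, repeated measures and rank ANCOVA. None relies on the negative binomial variance. They soften the consequence, as do the endpoint's secondary status and the fact that a conservative test creates no false claim. But they are sensitivity analyses: the planned interval and p-value stay uncorrected.

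**Conclusion.** The point holds as a mismatch between model and outcome, with a conditional consequence. It is certain from the text that the endpoint is capped at 7 and that the planned model has no ceiling and no variance protection. Under the assumed beta-binomial distributions, size lies between about 4% and about 10-12%. It is conservative (about 4-9%) with a dry share of roughly 0.30 or more and strong clustering, or a share near 0.60 with weak clustering. Power loss runs from about 0-4 points with moderate clustering to about 13-16 points with strong clustering. The figures assume the week-12 value as response, so they do not apply to a literal fit of the change from baseline. The effect is confined to one unadjusted secondary endpoint. The plan should be changed because the mismatch is definite, the possible loss is material and the remedy is cheap.

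**What to change.** In both SAP 6.4.2 and protocol 9.4.2, replace the model statement along these lines:

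- **Response:** number of dry days out of all classified (dry + wet) diary days at week 12/EoT. Where a value is carried forward, carry the count and its denominator together.
- **Model:** binomial regression with logit link and an overdispersion parameter (quasi-binomial or beta-binomial, named in advance).
- **Terms:** treatment, sex and region as factors; baseline dry-day proportion as covariate, which is defined when it is zero.
- **Denominator:** count a weekend day without leakage as dry, following the definition in SAP 5.2.5. The validity rule in SAP section 5 accepts a weekend day for incontinence only if a leakage was recorded, and read literally would drop such days.
- **Display:** keep the 7-day scale for descriptive summaries.

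The cost is one model statement in each document, with no new data, visits or sample size; SAP section 1 allows revision before hard lock. The effect becomes an odds ratio instead of a rate ratio. Calibration is improved but not exact: quasi-binomial size was 7.8-11.7% in the 28 scenarios and about 8-13% in a smaller run of 500 null trials per scenario.

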5 EFFICACY AND SAFETY ENDPOINTS

Data for the efficacy endpoints will be recorded on an e-diary. This e-diary consists of a:

- 5-day Weekday Diary (bladder diary, Monday Friday), which is used for a 5-day period to record micturition frequency and incontinence episodes, and
- 2-day Weekend Episodic Diary (Saturday and Sunday), which is used to record micturition frequency, incontinence episodes, (pee) volume measurements, and worst leakage severity.

A valid diary day for:

• "Volumes"

In the 2-day Weekend Episodic Diary, is any e-diary day for which at least one "Pee Volume" greater than 0 mL is recorded with complete date and time.

- "Micturitions"
- In 2-day Weekend Episodic Diary, is any diary day for which at least once "Pee Volume" greater than 0 is recorded.
- In 5-day Week Diary, is any diary day for which the response to the question "Number of times using the toilet during the day/night" is not missing.
 - "Incontinence episodes"
- In 2-day Weekend Episodic Diary, is any diary day for which at least:
 - One micturition ("Pee Volume" >0) and
 - One "Leakage" or "Pee in toilet and Leakage" are recorded.
- In 5-day Week Diary, is any diary day for which:
 - The response to the question "How was your day/night" is not missing.

A valid diary for an analysis visit is a diary with at least 4 valid diary days within that analysis visit window. If for more than 7 days the diary is filled in prior to a visit, only the last 7 days prior to that visit will be used for calculation of the efficacy endpoints.

The number of valid diary days: Count of the valid diary days during the 7-day diary period. Days of visits to the clinic will not be counted as valid diary days.

In the event that in the 2-day Weekend Episodic Diary there are two entries with the same collection date and time but with different times of entry on the device, the last entry (time) will be used for analysis.

For several of the secondary efficacy endpoints, diary data will be classified as either "daytime" or "nighttime", where "daytime" is considered to mean "between waking up in the morning and going to sleep later the same day or next day" and "nighttime" means "between going to sleep on a day and waking up on the same or next day".

Whether an entry into the 5-day Week Diary is done during daytime or nighttime is captured on this diary.

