5.2 Secondary Efficacy Endpoints

The following secondary efficacy endpoints, as derived from the e-diary, are the change from baseline to the end of the 12-week treatment period in children (5 to <12 years of age) in:

- Mean volume voided per 24 hours
- Maximum volume voided
- Mean number of daytime incontinence episodes per 24 hours
- Mean number of nighttime incontinence episodes per 24 hours
- Mean number of daytime micturitions per 24 hours
- Number of dry (incontinence free) days per 7 days

For all above secondary efficacy endpoints the value calculated from the e-diary period 7 days before visit 3/week 0/baseline will be regarded as the baseline value.

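### The dry-days analysis cannot be run on the full FAS as written: its response can be negative, its log baseline covariate is undefined at zero, and read literally weekend days count only when wet.

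*SAP*

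**What the plan says.** **Response.** SAP 6.4.2 applies the negative binomial model to "Change from baseline in the number of dry (incontinence free) days per 7 days" at the end of the 12-week period, and protocol 9.4.2 does the same. SAP 5.2 agrees: "The following secondary efficacy endpoints, as derived from the e-diary, are the change from baseline to the end of the 12-week treatment period", with dry days in the list that follows. Protocol Table 5 and SAP Table 1 instead name the number of dry days per 7 days at the end of treatment. SAP 5.2.5 derives a level only ("then the number of dry days per 7 days at Visit 7 will be calculated for a subject as"): 7 × Ddry/(Ddry + Dwet), provided more than 3 days are available.

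**Covariate.** The SAP adjusts for the log baseline rate, "e.g., the log of the ratio of dry days and number of diary days at baseline) as covariate". The protocol's version is "the log of the number of dry days divided by number of diary days at baseline". Neither says what happens at zero. The only zero-baseline rule is in SAP 5.3.1, which adds 0.5 to a zero count of daytime leakages for the responder endpoint.

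**Weekend days.** In SAP 5.2.5 a dry weekend day "is defined as a day where no 'Leakage' and no 'Pee in toilet and leakage' are reported". In SAP 5 a weekend day is valid for incontinence only if there is at least one micturition and "One 'Leakage' or 'Pee in toilet and Leakage' are recorded".

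**Other analyses.** SAP 6.4.2 uses the FAS, with and without LOCF, and adds: "The same analysis detailed in Section 6.4.1.3 will be performed for all the secondary efficacy endpoints on the FAS as sensitivity analysis".

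**The concern.** A model has to be defined for every child in its analysis set. Here two groups fall outside it: children with no dry day at baseline, who have no covariate value, and, if the response is a change, children who lost dry days. Software will stop or leave them out, and the plan chooses neither course. The first group has the worst baseline. The second is defined by its outcome, so losing it would select on response. Otherwise somebody must choose the response, the covariate and any exclusions after the plan is final.

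The weekend rule raises a different problem. It alters the value of the endpoint itself, at baseline and at week 12, and does more than change how often zeros occur.

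**Working it through.** The documents give no figure for this analysis, so there is none to reproduce. The 164 evaluable children of SAP 3 are used below only for scale. The leak distribution is assumed: independent Poisson leaks with mean m per day, the same for every child, so a day is dry with probability p = e^(−m).

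**1. Response.** With 0 to 7 dry days at each time, the change runs from −7 to +7. The negative binomial supports 0, 1, 2 and so on, so one negative value makes the likelihood zero.

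**2. The end-of-treatment value as rescaled.** 7 × Ddry/(Ddry + Dwet) is an integer whenever 7 days are valid. With 4, 5 or 6 valid days it is an integer only if no day or every day is dry: 1 of 4 gives 1.75, 1 of 5 gives 1.4 and 3 of 6 gives 3.5. Replacing the change by this level removes the negative values but does not produce a count.

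**3. Covariate.** log(0/7) is undefined. The share of children with no dry day in 7 is (1 − e^(−m))^7:
- m = 1: 0.632^7 = 0.040, about 164 × 0.040 = 7 children
- m = 2: 0.865^7 = 0.361, about 164 × 0.361 = 59 children

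Inclusion criterion 16 (protocol 5.1) requires on average at least one daytime leak per day over the 7 baseline days. SAP 7.2 suggests that entry criteria have since changed, so it is not imposed above. Simulation with it imposed, at the same fixed rates and treating leaks as daytime, gives 7% and 37%.

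**4. Mechanical check.** One data set of 164 children was simulated from an assumed distribution, giving 39 with no dry baseline day and 28 with a negative change.
- With the log covariate as written, the fit stopped with an error. Dropping the 39 leaves 125.
- With the change as response and the covariate repaired, the log-likelihood was minus infinity.
- With the end-of-treatment count as response and a covariate defined at zero, the model ran on all 164.

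**5. Weekend rule read literally.** A leak-free weekend day is not valid, so only weekdays can supply dry days and weekend days enter only when wet. With W wet weekend days, the value is 7 × Ddry/(5 + W), where Ddry is out of 5. Its mean is 35p × E[1/(5 + W)], against 7p if all seven days count.
- m = 0.5 (p = 0.6065): P(W = 0, 1, 2) = 0.368, 0.477, 0.155, so E[1/(5 + W)] = 0.1752. The mean is 35 × 0.6065 × 0.1752 = 3.72, against 7 × 0.6065 = 4.25.
- m = 1 (p = 0.3679): P(W = 0, 1, 2) = 0.135, 0.465, 0.400, so E[1/(5 + W)] = 0.1617. The mean is 35 × 0.3679 × 0.1617 = 2.08, against 7 × 0.3679 = 2.58.

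Zero dry days also become more common: (1 − e^(−m))^5 is 0.101 at m = 1 and 0.483 at m = 2, against 0.040 and 0.361 above.

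**The case against.** The strongest reply is that the intention is clear enough. The change wording may simply have been carried over from the neighbouring endpoints, the covariate is introduced with an e.g., and a sensible programmer would model the week-12 number with a small constant in the log. This is one secondary endpoint, and the analyses carried over from SAP 6.4.1.3, including the rank ANCOVA, can be run without a log baseline rate or a negative binomial likelihood. The last point stands and limits the consequence. The rest does not rescue the specification: the analysis paragraphs of both documents say change, the only covariate named is the undefined one, and a constant borrowed from another endpoint is not prespecified here.

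Three further cautions are fair.
- SAP 5.2.5 is weak evidence of a conflict over the response, because SAP 5.2.1 to 5.2.4 also derive visit values that SAP 5.2 then turns into changes. The contradiction rests on the objectives tables.
- A reader might infer a definite loss of power. The documents give no leak distribution and no expected effect on leaks, and nowhere instruct that children who worsened be removed, so no power figure can be supported.
- The protocol reviewed is version 2.0, while the SAP allows for version 3 or higher. Whether protocol 9.4.2 still reads this way cannot be settled here.

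**Conclusion.** The point holds. As written, the main dry-days analysis is undefined for any FAS child with no dry baseline day and for any child whose dry days fell. Switching to the rescaled end-of-treatment value would still leave non-integer responses with 4 to 6 valid days. The weekend conflict is a separate defect in the endpoint's definition: it lowers the value and adds zeros.

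That the analysis fails follows from the text; how many children it affects does not. The 4% and 36% zero-baseline shares, and the fall in the mean of about half a day (4.25 − 3.72 = 0.53 and 2.58 − 2.08 = 0.50), rest on the Poisson assumption with a common leak rate and complete diaries.

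A reader might conclude that the trial's efficacy result is compromised. The documents do not support that: the primary endpoint, its ANCOVA and the sample size do not use this model. This should be fixed, but it does not threaten the trial.

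**What to change.** Before database hard lock:

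1. Make end-of-treatment dry days the response. Model dry days out of valid diary days with an overdispersed binomial model. If the negative binomial is kept, use the raw dry-day count with a log(valid days) offset. The ANCOVA that SAP 6.4.2 applies to its other secondary endpoints is also acceptable.
2. Use a baseline covariate defined at zero, such as the untransformed baseline proportion of dry days.
3. State in SAP 5 that a completed weekend diary day with no leakage is a valid dry day, so that it agrees with SAP 5.2.5. The daytime incontinence mean in SAP 5.2.3 uses the same valid days and should be checked at the same time.
4. Align the wording of SAP 5.2, SAP 6.4.2 and, if still current, protocol 9.4.2 with the objectives tables.

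The cost is a small SAP revision, which SAP 1 allows before hard lock, and a change of stated model for one secondary endpoint. If protocol 9.4.2 still carries this wording, changing it has to be documented as an amendment under protocol 12.1. No new data are needed.
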